While the prevalence of drug use is similar across ethnicity, except for Asian populations who have a lower prevalence (OR 0.39; 95% CI 0.19 to 0.81), the proportion of those receiving treatment is far lower, 5% of ethnic minorities versus 89% White British. Reasons for this disparity include lack of awareness of available services, lack of culturally sensitive services and a lack of trust stemming from previous negative experiences with services (Pinto et al., 2024). Furthermore, the complexities of intersectionality's of marginalised communities also play a role in an individual's openness to engage, and experience of, a range of support and statutory services from healthcare to the justice system (Healy and Colliver, 2022).

Multidimensional family therapy (MDFT) is widely delivered across the United States, Netherlands, Belgium, Sweden, Finland, Lithuania and Aruba, although there is no current MDFT provision in the UK. MDFT is an integrative, family-based, multiple systems-oriented intervention specifically designed to address adolescent problems including substance use, mental health, aggressive and violent behaviour and delinquency (Liddle, 1991, Liddle et al., 2005). MDFT's aim is to reduce substance use, improve mental health and enhance developmental functioning across several behavioural domains:

- 1. the adolescent domain helps adolescents to engage in treatment, regulate their emotions, communicate with, and relate effectively to, their parents and other adults, and to develop social competence and alternative behaviours to drug use.
- 2. the parent domain engages parents in therapy, increases their behavioural and emotional involvement with their children and improves parental practices.
- 3. the family interactional domain focuses on reducing conflict and improving emotional attachments and patterns of communication and problem-solving using multi-participant family sessions.
- 4. the extrafamilial domain fosters family competency within all social systems in which the adolescent participates.

The intervention is manualised and delivered by trained therapists through individual and family sessions.

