Wellbeing will be assessed using the Short Warwick-Edinburgh Mental Well-being scale (SWEMWBS; (Clarke et al., 2011)). SWEMWBS is a 7-item, self-completed scale addressing different aspects of eudemonic and hedonic mental health wellbeing. The scale is validated for adolescents and demonstrates good internal consistency (Ng Fat et al., 2017), and discriminant, construct and convergent validity (McKay and Andretta, 2017, Ng Fat et al., 2017).

We will use questions derived from a Client Service Receipt Inventory (CSRI; (Coulton S et al., 2023) to assess school, work and criminal justice involvement over the previous 6-months. All these outcomes will be assessed at baseline and again at month 6.

To explore the mechanism of change we aim to assess changes in domains that are key targets of MDFT. The Brief Family relationship Scale (BFRS; (Fok et al., 2014)) will be used to assess family conflict and cohesion. Motivation to change will be assessed using the readiness to change ruler (RR; (Maisto et al., 2011)). Self-efficacy will be assessed using the short Situational Confidence Questionnaire (SCQ-8;(Breslin et al., 1998)). Positive and negative Expectancy will be assessed using a four-item expectancy measure (SUE; (Montes et al., 2019)).

Secondary outcomes will be assessed at baseline and at the 6-and 12-month follow-up points and have established psychometric properties in adolescent population. Therapeutic alliance will be assessed using the revised Therapeutic Alliance Scale for Children (TASC-r; (Shirk and Saiz, 1992)) at the 6-month follow-up only.

All outcome measures have been used previously in adolescent populations, and we estimate the outcome data set takes on between 10 and 20 minutes to complete.

Table 4: Core outcomes and the time of data collection.

Outcome	No of items	Baseline	Six months
Stratification			
Global Assessment of Individual Need – short screen (GAIN-SS)	5	✓	
Covariate			
Single Substance Use Question – 28 day (SUSQ28)	1	✓	
Primary			
Time Line Follow-Back – 28 (interview)			✓
Secondary			
Self-reported delinquency (SRDS) ¹	36	✓	✓
Strength and Difficulties (SDQ) ¹	25	✓	✓
Wellbeing (SWEBWMS)	7	✓	✓
Family cohesion and conflict (BFRS)	15	✓	✓
Alcohol and substance use problems (ESPAD)	8	✓	✓
Client Service Utilisation (CSRI)	8	✓	✓
Exploratory			
Motivation to change (RR)	1	✓	✓
Substance use expectancy (SUE)	4	✓	✓
Substance use efficacy (SCQ8)	8	✓	✓
Therapeutic Alliance (TASC-r)	12		✓

¹SRDS and SDQ are YEF core outcomes.

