Fractional regression analysis will be performed to model the relationship between prerandomisation factors, and demographics on observed outcomes at 6 months, for the primary outcome. Interaction terms with allocation arm will be included in the analysis, and a significance level of 0.1 will be used to determine which factors are to be included in the model. Pre-randomisation factors will include ethnicity, sex, age, IMD decile, severity of substance use, and baseline family cohesion, motivation, self-efficacy and expectancy. This analysis will be augmented by an additional analysis including participants in the intervention arm only using the same pre-randomisation factors but also including process measures of adherence, intervention fidelity, and therapeutic alliance.

Latent class approaches will be used to explore the hypothesised mechanism of change exploring changes over time in family cohesion, motivation to change, self-efficacy and substance use expectancy.

Qualitative analysis

The aim of the qualitative analysis in the efficacy study will be to link samples by grouping, comparing, and contrasting responses from all data sources to address the research questions. This linking of data allows for a concentrated and more meaningful analysis of the influence of the programme through its contexts and mechanisms, and of its perceived impact through a thematic blending of data elements. The key questions that we will seek to answer at this stage will include:

- Are there any residual or new external or logistical issues impacting referral, intervention delivery, or attrition?
- What are young peoples' positive and negative experiences of the intervention and how do these fit with providers' perceptions?
- At what points in the intervention have these experiences occurred?
- Are there practices associated with the intervention that can be amended to further increase its acceptability and impact?
- Do stakeholders see the intervention as impacting participant's behaviour?
- In what ways has substance use and offending been impacted?

This provides an opportunity to explore the perceptions of the intervention from the point of view of a variety of stakeholders using Normalisation Process theory (NPT; (Finch et al., 2012). Bracketing, reflexivity, and member checking will be employed to ensure trustworthiness and rigour.

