An aspect of our qualitative work with key stakeholders involves examining participants' positive and negative experiences of the referral process and intervention, exploring how these perspectives concur with those who deliver the intervention, explore at what points negative and positive experiences are at their greatest and what steps could be taken to ameliorate these experiences to improve the delivery and acceptability of the intervention.

Exploring Adaptation

The mechanism of change will be explored using a latent class mediation model. Exploring factors that impact on the mechanism of change will be assess the relationship between prerandomisation factors and observed outcomes at 6 months. Pre-randomisation factors include sex, age, ethnicity, IMD decile, family cohesion, motivation to change, self-efficacy and substance use expectancy.

In addition to quantitatively understanding the mechanism of action, the qualitative analysis will provide an opportunity to explore the perceptions of the intervention from the point of view of a variety of stakeholders. The analysis will allow us to explore what elements of the interventions are useful and what elements are unnecessary, issues around how the interventions are planned and implemented and the perceived barriers or facilitators of implementation in usual practice.

Through a detailed exploration of the key dimensions, we plan on stating our logic model at the start of the project, and revise this again at the end of the internal pilot stage. The logic model will incorporate the qualitative research exploring stakeholder perceptions of acceptability and usefulness, hindrances and facilitators associated with the process and intervention but will also combine quantitative analysis exploring adherence, dosage, fidelity, and mediators associated with behaviour change. This mixed methods synthesis will enable

us to understand what works, how it works, when it works and for whom it works and provide a detailed elaboration of the mechanisms and processes through which it works.

Exploring Factors Affecting Implementation

Interviews with intervention delivery partners and key stakeholders, including those delivering similar substance use services to CYP, will explore how sustainable the intervention is in its current format. What key challenges were experienced and what changes might be necessary to roll out the intervention more widely.

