A key aspect of MDFT involves building a strong therapeutic alliance with young people and their parents/ carers as the foundation of achieving behaviour change. Therapeutic alliance is assessed using the Therapeutic Alliance Scale for Children (TASC-r; (Shirk and Saiz, 1992). Where young people feel included in decision making and experience a sense of positive collaboration with the therapist and families experience consistency in the support

Young people develop an enhanced motivation to change their substance using behaviour, assessed using the readiness ruler (RR; (Maisto et al., 2011). They develop better strategies for managing situations where they would previously engage in substance use, assessed using the situational confidence questionnaire (SCQ; (Breslin et al., 1998) and they have a better understanding of their own strengths and a greater appreciation of the negative aspects of substance use, assessed using the substance use expectancy measure (SUE; (Montes et al., 2019). Families experience greater communication, less conflict and are empowered to solve problems

collaboratively, assessed using the brief family relationship scale (BFRS; (Fok et al., 2014)).

In the study the influence of these mechanisms on substance use and offending will be explored using a latent class mediation model approach that aims to identify implicit subgroups among the study population based on their response to a set of process (mechanistic) variables hypothesised to influence change. These variables are assessed at baseline, prior to randomisation and again at 6-months post-randomisation.

Short term outcomes

Short term outcomes are measured at baseline and again at 6-months post-randomisation.

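### The mechanism analysis names cohesion as its only family variable, while the theory of change names communication and conflict; the lists should be reconciled

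*Protocol*

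**What the plan says.** **Where cohesion stands alone.** Under Exploratory analysis, the latent class work on the mechanism of change is described as "exploring changes over time in family cohesion, motivation to change, self-efficacy and substance use expectancy". The regression in the same section includes among its pre-randomisation factors "baseline family cohesion, motivation, self-efficacy and expectancy". In the process evaluation, Exploring Adaptation ends its list of pre-randomisation factors with "IMD decile, family cohesion, motivation to change, self-efficacy and substance use expectancy".

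**Where the family target is wider.** Study rationale and background says that "the family interactional domain focuses on reducing conflict and improving emotional attachments and patterns of communication and problem-solving". Under Secondary outcomes, the BFRS is introduced among the mechanism measures and "will be used to assess family conflict and cohesion". Appendix I, Mechanisms, states the family part of the theory of change: "Families experience greater communication, less conflict", with joint problem-solving, all assessed on the BFRS. The next paragraph commits the mechanisms just listed to a latent class mediation model, using process variables measured at baseline and six months.

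**What is collected.** Table 4 schedules the BFRS at baseline and six months. The form in Appendix IV prints three separately headed parts: cohesion (items 1–7), expressiveness (8–10) and conflict (11–16).

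**The concern.** The Exploratory analysis section fixes a set of mechanism variables that differs from the set in the theory of change. It names the one family construct that Appendix I does not mention in its mechanism statement, and it omits the two that Appendix I does name.

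This matters because the mechanism results have a set use. ERQ11 and the Adaption rows of Table 5 feed them into revision of the logic model and the theory of change, and the process evaluation asks how the observed causal pathways compare with the proposed ones. Latent classes are built from the variables that enter the model. If conflict and expressiveness are not entered, a family pathway that runs through them can appear only as far as cohesion tracks them, and a weak result could be misread as evidence against the family part of the theory. If the analyst adds conflict later, after seeing data, the choice would look post hoc.

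**Working it through.** The protocol gives no figure on this point, so there is none to reproduce. The check is a comparison of the text, followed by an illustration of what a proxy costs.

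**1. Comparison**

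| Place in protocol | Role | Family variable(s) |
|---|---|---|
| Exploratory analysis, latent class work | mechanism | cohesion |
| Exploratory analysis, regression | pre-randomisation factor | cohesion |
| Exploring Adaptation | pre-randomisation factor | cohesion |
| Exploring Adaptation, mediation model | mechanism | not listed |
| Secondary outcomes | measure for mechanism of change | conflict, cohesion |
| Appendix I, Mechanisms | mechanism, committed to the mediation model | communication, conflict, problem-solving |

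The first and last rows both say what enters the latent class analysis of mechanism, and they differ. Cohesion is not an established label for the whole scale: Table 1 (baseline) and Table 4 write cohesion and conflict as two constructs, and Appendix IV prints them under separate headings.

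**2. Illustration**

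*Input from the protocol:* 182 per arm, 364 in total (Table 3).

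*Assumptions, not from the protocol:*
- MDFT shifts conflict by 0.4 SD.
- The conflict–outcome slope is 0.3.
- All mediation runs through conflict.
- Cohesion has within-arm correlation ρ with conflict (absolute value) and moves only through that correlation.
- The test is a single-mediator joint-significance test, two-sided 0.05. This is simpler than the planned latent class model.

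*Formulas when cohesion is analysed in place of conflict:*
- MDFT-to-mediator path: 0.4ρ, with SE = √(2/182) = 0.1048
- Mediator-to-outcome path: 0.3ρ, with SE = √(1 + 0.09(1 − ρ²)) / √364
- Indirect effect: 0.4ρ × 0.3ρ = 0.12ρ²
- Power ≈ Φ(z₁ − 1.96) × Φ(z₂ − 1.96), where z₁ and z₂ are each path divided by its SE

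| ρ | Indirect effect | z₁ | z₂ | Power, formula | Power, simulated (3,000 runs) |
|---|---|---|---|---|---|
| 1.0 (conflict itself) | 0.120 | 3.82 | 5.72 | 97% | 97% |
| 0.8 | 0.077 | 3.05 | 4.51 | 86% | 85% |
| 0.6 | 0.043 | 2.29 | 3.34 | 58% | 57% |
| 0.4 | 0.019 | 1.53 | 2.21 | 20% | 20% |
| 0.2 | 0.005 | 0.76 | 1.10 | 2% | 2% |

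Worked row, ρ = 0.4: z₁ = 0.16/0.1048 = 1.53 and z₂ = 0.12 × 19.08/1.037 = 2.21. Power ≈ Φ(−0.43) × Φ(0.25) ≈ 0.33 × 0.60 ≈ 0.20.

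The indirect effect shrinks with the square of ρ. A close proxy costs little and a moderate one costs most of the power. The documents do not say which case applies.

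**The case against.** - **The protocol as a whole does not leave conflict out.** A reader might infer that it tests cohesion only. Appendix I rules that out, because it commits the communication and conflict mechanisms to the mediation model. This stands, and it makes the problem a contradiction between sections and not a general omission.
- **Exploring Adaptation does not restrict the mediators.** It says that "The mechanism of change will be explored using a latent class mediation model" and lists no mediators; its cohesion entry is a pre-randomisation factor. Table 5 also leaves the mediators open. This stands, so the section needs alignment only in its factor list.
- **The BFRS is not idle.** A reader might count the nine expressiveness and conflict items out of sixteen and conclude that they are never used. Table 4 lists the BFRS among the secondary outcomes, for which regression analyses are planned, so the documents do not support that.
- **Cohesion may be shorthand for the instrument.** The four labels in the Exploratory analysis list follow the order in which the four instruments are introduced, and the conflict items are marked for reverse scoring. This is possible but not secure, given the separate naming in Tables 1 and 4 and Appendix IV. If shorthand was meant, the wording still needs correcting.
- **The SAP may settle it.** Details of a latent class model often belong there. But the protocol is not silent: it fixes a list, and a SAP can follow that list or Appendix I, not both.
- **The analysis is exploratory**, and revision of the logic model also draws on qualitative work. This stands and limits the weight of the point.

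**Conclusion.** The concern holds as an internal contradiction over which family variables enter the mechanism analysis, with the same narrow choice repeated in two lists of pre-randomisation factors. An analysis that followed the Exploratory analysis list would examine conflict and communication only through cohesion.

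The size of the loss cannot be fixed from the documents. Under the assumed paths, power falls from about 97% with conflict itself to about 85% at a correlation of 0.8 and about 20% at 0.4. These figures illustrate the dependence on the correlation and do not predict this trial's performance, since the planned method differs.

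A reader might go further and infer that a family pathway is almost certain to be missed. That would need a very weak correlation, or an MDFT effect on conflict with none on cohesion. The protocol supports neither. It also says that MDFT strengthens emotional attachment within the family, which is close to what the cohesion items ask about. The primary result is unaffected whichever list is followed.

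**What to change.** In Exploratory analysis, replace family cohesion in the latent class mechanism list with the BFRS cohesion, conflict and expressiveness subscales, which brings it into line with Secondary outcomes and Appendix I. Use the same set in the pre-randomisation factor lists in Exploratory analysis and Exploring Adaptation. Make the change before outcome data by arm are examined.

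Nothing is added for participants, because the BFRS is already scheduled at baseline and six months. The cost is one or two more exploratory variables. In the regression, where interactions with arm are screened at 0.1, two further factors with one interaction term each add 2 × 0.1 = 0.2 expected chance selections if neither matters.

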Staff at Barnardo's will screen referrals to ensure they are consistent with the study inclusion and exclusion criteria and take informed consent. The principle of Gillick consent will be employed by staff trained in assessing Gillick competence to assess whether participants are mature and intelligent enough to make their own informed decisions. As a rule, young people aged 13 years or more, of average intelligence, are considered Gillick competent. Unless there is a specific reason not to do so, parents/ carers will be informed of the young person's participation in the study. Where consent cannot be taken using the Gillick principle, consent will be sought from a person with parental responsibility, in this scenario if a parent/ carer provides consent the young person will also have to provide assent to ensure there is no parental coercion to participate. Parent/carer consent is not required at the start of delivery. MDFT therapists will work with the young person to build their trust in the process and comfort with seeking parental/carer consent. They will also work to identify a trusted adult that could take the place of a parent/carer where needed. Broadly speaking, we would expect parents to be approached within a month of the young person starting MDFT. Giving young people the time and space to decide whether to approach a trusted adult, who it may be, and how they may approach them is crucial to the rapport building process.

It is anticipated that 60% of the referrals will come from Bristol and 40% from Newport, based on the relative population sizes. This means that 4 therapists will be recruited in Bristol and 3 in Newport. Based on our delivery in Bristol to young people being harmed in their communities through substance use, serious violence, and exploitation, we receive referrals showing a disproportionate percentage of racially minoritised young people. Following discussion with our referring partners in both LAs, we believe this pattern will be reflected in the MDFT pilot.

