We propose to conduct an analysis to explore the role compliance, therapeutic alliance, fidelity and interventionist impact on the outcomes observed. A regression model, with the primary outcome as dependent variable and adjusting for key covariates identified will be conducted. This will allow for a quantification of what dimensions of the intervention are associated with outcomes and will enable an exploration of whether certain domains are more important than others and should be emphasised in the intervention delivery and, by extension, the training. Allied to this, the perception of therapeutic alliance will provide an insight into whether therapist communication style influences outcomes.

Exploring Non-compliance

In addition to this we would want to explore whether certain factors are associated with non-compliance to identify potential clusters of participants who do not comply. We will conduct a latent class analysis to identify clusters associated with non-compliance, this will enable an exploration of whether there are groups of participants who are harder to reach than others and by augmenting this quantitative approach with targeted qualitative interviews with young people and interventionists, enable the wider research group to explore what adaptations may be necessary to increase accessibility and compliance.

Exploring Reach

A key area to explore in terms of reach is whether all potential participants are being identified and referred to participate in the study. We will conduct specific research to explore for differences in potentially eligible and referred participants in each site with a key focus on ethnic and culturally appropriateness of both the referral mechanism and intervention delivery. Through the qualitative work we will also focus on reasons why some may not want to engage with the intervention. This information will allow us to quantify any inherent biases associated with referral in terms of key demographics, such as age, sex or ethnicity and to further explore these with our stakeholder interviews. This approach will enable us to understand how generalisable the study results are and whether changes need to be made to referral pathways or intervention delivery to make the population more inclusive.

Exploring Responsiveness

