The qualitative aspect of the work will involve the collection of narrative accounts from a range of individuals using semi-structured interviews. These will be collected from young people participating, carers and staff involved in the programme delivery and professionally associated with the young people. Professionals will be sampled purposefully from the different staff groups, and young people will also be purposefully sampled. Synthesis of these data sources will allow a detailed overview of the implementation and processes associated with successful delivery of the intervention.

Table 5: IPE methods overview

IPE Question	Data collection methods	Participants/ data sources (type, number)	Data analysis methods	Research questions addressed	Implementation/ logic model relevance
Fidelity/ adherence/ differentiation/ quality	Participant survey, therapeutic alliance, session data	400 participant surveys and TASC-r	Regression analysis	Quantification of the role fidelity, and quality plays in the outcomes observed	Better quality interventions that involve better alliance and communication between young people and practitioners are associated with better outcomes.
Compliance	Session planned and attended, outcome data	400 participant surveys, process database	Complier Average Causal Effect analysis	Estimation of the role compliance plays on observed outcomes at variable thresholds	Greater frequency of intervention is associated with better outcomes

	Factors associated with non- compliance	400 participant surveys, process database	Latent Class Analysis	Explore factors associated with non-compliance	Create targeted opportunities to reduce non-compliance and maximise acceptability.
Reach	Cohort Approach	Data on all young people referred to the service compared with data for those who consented	Logistic regression whether the model with intervention consent as the dependent outcome referred to the services		Identify any potential issues with accessibility.
	Qualitative interviews with service leads and key stakeholders	10 semi- structured interviews	Transcribing and inductive analysis to allow themes to emerge naturally	Identify any populations that experienced limited accessibility and the potential reasons for this.	Identify issues with accessibility and how these may be addressed

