As was the case during the co-design phase, a group of young people (13-17 to reflect the age groups involved in the study) will be convened monthly. This group (YPAG) will advise on matters pertaining to recruitment (and materials) and the cultural appropriateness of both the intervention and evaluation activities. Involvement will take the form of a monthly group meeting in which specified questions from the wider project team and Equity Team will be brought to the group for discussion. In addition, each session will allow dedicated space for young people to raise any issues identified that may not have been considered already to ensure the avoidance of 'unknown unknowns' (Wynne, 2015) and ground the study within real rather than 'imagined publics'. (Wynne, 2015) Young people that choose to take part in the YPAG will be remunerated £25 (via voucher) for their time, in line with the National Institute of Health and Care Research (NIHR) guidance on public participation in research (NIHR, 2022). The YPAG will be representative of the communities where the research takes place in terms of ethnicity and will purposively sample to ensure diversity for YP with SEN,

LAC and neurodiverse YP. The YPAG will include young people of the target age who have experience of substance use. The YPAG will be managed by a specific member of the research team who has extensive experience in working with YPAG and associated safeguarding issues. Meetings will take place on-line to avoid any potential for iatrogenic effects.

The study has been designed to minimise sources of bias. This includes having enough participants to encompass a diverse population that is representative of the target population, minimising inclusion, and exclusion criteria to reduce barriers to participation, ensuring randomisation is conducted independent of the research team, flexibility in conducting baseline and follow-up assessments to allow those with literacy difficulties to complete assessments verbally if required.

We will actively monitor recruitment on key ethnic, socio-cultural and inclusion parameters and where differences occur in the numbers eligible and the numbers consenting, we will explore the reasons why using qualitative interviews to provide an insight into the cultural and ethnic acceptability of the intervention.

We will conduct qualitative and quantitative analysis to explore the role inequality, ethnicity, and socio-economic disadvantage plays in the outcomes observed.

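### Table 5's Reach regression models consent among everyone referred, so a difference in eligibility between groups could appear as a difference in consent, or hide a real one

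*Protocol*

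**What the plan says.** Table 5 (IPE methods overview) has two Reach rows. The quantitative one gives its data source as "Data on all young people referred to the service compared with data for those who consented" and its method as logistic regression with "consent as the dependent outcome". The analysis and research-question cells of that row are run together in the text I have, so I rely on the data-source cell, which is intact, and on the named outcome. The second row is 10 semi-structured interviews with service leads and key stakeholders.

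The order of events is in the Participants section: "Staff at Barnardo's will screen referrals to ensure they are consistent with the study inclusion and exclusion criteria and take informed consent". Figure 3 agrees: eligibility and frequency of use are checked once the referral form has been received. Referral can rest on suspected use, whereas inclusion criterion 3 needs at least four occasions of use in 28 days and two exclusion criteria also apply.

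The Exploring Reach text describes a different question: "A key area to explore in terms of reach is whether all potential participants are being identified and referred to participate in the study". It promises to "explore for differences in potentially eligible and referred participants in each site" and says the information will allow the team to "quantify any inherent biases associated with referral in terms of key demographics, such as age, sex or ethnicity".

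The Design section plans monitoring that includes young people who are eligible but refuse. The Diversity, equity and inclusion section plans interviews "where differences occur in the numbers eligible and the numbers consenting".

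**The concern.** Among all referrals there are three outcomes: ineligible, eligible and declined, eligible and consented. A regression of consent on that cohort merges the first two. A group that is more often screened out then looks like a group that more often refuses. If the two steps run in opposite directions, a real difference in willingness can disappear.

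The protocol intends to use Reach results to judge generalisability and to decide whether referral pathways or delivery should change, with particular attention to ethnicity and culture. Screening criteria, consent materials and referral routes call for different remedies, so it matters which step a coefficient describes.

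A second gap concerns the step before referral. A dataset that starts at referral contains nobody who was not referred, so it holds no information on who is missed.

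**Working it through.** **Inputs**
- Consent among the eligible: c = 0.80 (Sample size calculations).
- Referrals and recruits: 500 and 400 (Table 2, last column).
- Share of referrals that are eligible: e. The protocol gives no planning value, so every value below is an assumption.

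**The plan's own figure.** 500 × 0.80 = 400, so Table 2 reproduces. Because 80% is the consent rate among the eligible, Table 2 leaves no room for ineligible referrals (e = 100%).

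**Who the modelled non-consenters are.** The share who are in fact ineligible is (1 − e) / (1 − c·e):

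| e | 1 − c·e | Ineligible share of non-consenters |
|---|---|---|
| 100% | 0.20 | 0% |
| 90% | 0.28 | 0.10/0.28 = 36% |
| 80% | 0.36 | 0.20/0.36 = 56% |
| 70% | 0.44 | 0.30/0.44 = 68% |

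**A spurious difference.** Both groups consent at 80% when eligible. The probability of the modelled outcome is c·e.
- Eligibility 95% v 80%: 0.76 v 0.64. OR = (0.64/0.36) / (0.76/0.24) = 1.778/3.167 = 0.56.
- Eligibility 90% v 75%: 0.72 v 0.60. OR = (0.60/0.40) / (0.72/0.28) = 1.500/2.571 = 0.58.
- Among the eligible only: 0.80 v 0.80, OR 1.0 in both cases.
- Equal eligibility: OR 1.0 under either denominator.

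**A masked difference.** Consent among the eligible is 85% v 75%: OR = (0.85/0.15) / (0.75/0.25) = 5.667/3.000 = 1.89. With eligibility of 75% v 85%, the modelled outcome is 0.85 × 0.75 = 0.6375 and 0.75 × 0.85 = 0.6375, so OR = 1.00.

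**The referral step.** The aim in Exploring Reach needs a comparison of referred with potentially eligible but non-referred young people. The quantitative Table 5 row contains only the referred, and restricting it to eligible referrals does not change that. The text promises "We will conduct specific research to explore for differences in potentially eligible and referred participants in each site" but names no data source for it. The only other Reach row is the interviews, which do not produce an estimate.

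**The case against.** Four points can be made against this.

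1. **Table 5 is a one-line summary, and detail may sit in an SAP.** This holds for the predictor list and the coding. It does not hold for the cohort and the outcome, which the protocol states and nowhere restricts to eligible referrals.

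2. **Uptake among all referred is a legitimate measure of reach.** This stands. The row aims to find accessibility problems, and the equality impact assessment (Appendix III) raises the possibility that the way eligibility is defined could miss girls and young women. Overall uptake should be kept, but one odds ratio for it does not show which step is responsible.

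3. **Eligible-versus-consenting is monitored elsewhere.** This is true of the Design and Diversity, equity and inclusion sections, and the pilot analysis estimates the proportions eligible and consenting. A reader of the regression would have those figures alongside. They lessen the risk of misreading but do not alter the specified model.

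4. **The illustration is assumed.** This stands. Table 2 implies no ineligible referrals, and on those figures the artefact is nil. The background section reports similar drug-use prevalence across ethnic groups apart from a lower one in Asian populations, so the documents do not support any particular eligibility gap by ethnicity. I give no probability of a false-positive finding, because group sizes among referrals are not stated; the 35% minoritised share is an estimate for participants.

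A reader might also infer that the referral question cannot be answered at all. The documents do not support that: the promised specific research is not tied to this regression, and the interviews can inform the question qualitatively. What is missing is a data source for quantifying it.

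**Conclusion.** The concern holds in a limited form. As written, the Reach regression mixes ineligibility with refusal. Whether this distorts a group comparison depends on eligibility differing between the groups: under the assumed 95% v 80%, equal consent appears as an OR of 0.56; with equal eligibility and equal consent, the OR is 1.0. It would go too far to infer that the equity conclusions will be wrong, since the protocol gives no eligibility rates and plans descriptive monitoring of eligible refusers.

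The promise to quantify referral bias has no named quantitative source behind it, and the Table 5 cohort cannot supply one.

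Both points belong to the process evaluation. Neither affects the primary result. The case for change is that a clearer analysis is available at little cost.

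**What to change.** **Table 5, quantitative Reach row.** Keep overall uptake among all referred as a descriptive reach measure. Replace the single regression with two steps that use the same predictors and site:
1. eligible versus not, among referrals whose eligibility was assessed;
2. consented versus declined, among those who meet inclusion criteria 1 to 3 and no exclusion criterion. Criterion 4 must be left out of this definition because it is itself willingness to consent.

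Report separately those who decline before eligibility is known. Figure 3 has eligibility checked and interest gauged in the same contact, so some such cases are likely.

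**Exploring Reach text.** Limit the statement on quantifying referral bias to what the interviews and a coarse comparison with the planned site demographic data pack (Appendix III) can support, unless a source on non-referred young people is named. The pack is a general population overview, not a count of potentially eligible young people, and the protocol mentions no referral-partner caseload counts.

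**Cost.** One extra regression, a revised table row, and a record of the stage and reason for each non-entry. Step 2 has a smaller denominator than the referred cohort. If 400 are recruited at 80% consent, step 2 has 400/0.80 = 500 young people, against 500/0.90 = 556 referrals at an assumed 90% eligibility or 500/0.80 = 625 at 80%.
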